6.2 Secondary Endpoints

Secondary endpoints will include the following:

1. Cognitive and Language Scales of the Bayley-III at 18 months of age
2. Total maturation score (TMS)
3. Volumes of whole brain, white matter, gray matter and myelinated white matter (VMWM)
4. Presence of PVL on early post-natal brain MRI (categorical y/n)
5. Presence of PVL on early post-operative brain MRI (categorical y/n)
6. PVL Volume on early post-natal brain MRI
7. PVL Volume on early post-operative brain MRI
8. Compliance with progesterone regimen
9. Compliance with pre- and post-natal MRI's
10. Failure to return for 18 month neurodevelopmental evaluation.

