6.3.2 Efficacy Analysis

The primary analysis will be intent-to-treat and will estimate differences between group means and their associated confidence intervals. In parallel we will test the null hypothesis that treatment has no effect on each of three outcomes. Because of its clinical relevance, the study is primarily designed to provide an estimate of possible effect sizes for the Bayley-III Motor Scale at 18 months. Important information will also be provided on effect sizes for the Bayley-III Cognitive and Language Scales at 18 months, as well as total maturation score (TMS) and volume of myelinated white matter (VMWM). The analysis will use a two-sided two-sample T-interval (estimation) or T-test (hypothesis testing). The confidence level will be set at 90% and the Type I error at 10%. Normality will be assessed and a transformation, or alternatively a non-parametric test, will be used if needed.

Based on our earlier work, the occurrence of PVL, both pre- and post-operatively, has a complex distribution. At both time points, when occurrence of PVL is considered a categorical outcome, there are patients with no evidence of PVL (PVL=0), as well as patients with varying amounts of PVL (PVL=1). When occurrence of PVL is considered as a continuous variable (volume of PVL), there is a mixture distribution with a peak at zero and the remainder of

patients demonstrating a continuous highly skewed distribution. Thus it is of interest to know whether the prevalence of PVL (categorical outcome) prior to surgery and post-surgery differs between treatment groups (intention to treat). It will also be of interest to know if the volume of PVL (continuous outcome), among those who have PVL at baseline, differs between treatment groups, both at baseline and post-operatively.

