In the secondary analyses, we will use an exact binomial confidence interval to estimate differences between groups in the percent of subjects with PVL pre-operatively and the rate of increase post-operatively. The null hypothesis that treatment does not reduce the frequency of occurrence of PVL pre-operatively and the rate of increase post-operatively will be tested using Fisher's Exact test. The confidence level will be set at 90% and the Type I error at 10%. The PVL data can also be modeled in a more unified approach using mixture models, where the categorical data for patients with no PVL, and the continuous data for patients with evidence of PVL are modeled jointly.⁸⁸ In addition to these analyses, we will describe compliance, both with treatment and with MRI tests, as well as determine loss to follow-up for the 18 month time point. We will secondarily model TMS, VMWM and the Bayley-III Cognitive and Language Scales as a function of treatment, as well as other potential predictors of fetal brain maturation and development including: gestational age, type of CHD, ethnicity, age at surgery, operative management variables, maternal education and socioeconomic status. Presence of 22q11 deletions or other identified genetic anomaly and apo-lipoprotein E (*APOE*) genotype will be included as covariates in the analysis of the Bayley-III scores.

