Table 1 shows that for the Bayley-III Motor Scale, assuming 40 evaluable subjects per treatment group, and an SD of 15, the $\frac{1}{2}$ width of a two-sided 90% confidence interval on the mean difference is expected to be 5.6. Thus, for example, if the mean difference is 6.0 units, a clinically relevant value for this population, the 90% two-sided confidence interval is expected to be on the order of (0.4, 11.6), suggesting that while only a minor effect cannot be ruled out, important positive effects of progesterone appear possible. In contrast, if there is no effect of progesterone we expect an interval centered around zero with i.e. (-5.6, 5.6). This initial study will thus provide important information about the magnitude of the effect of progesterone, and an indication of whether it is worthwhile to proceed with further trials. For TMS, results from [name] (personal communication) estimated the mean (median) value of TMS in a similar cohort to be 10.1 (10.0) with a standard deviation (SD) of 1.06 and range of 8.0 to 13.5. Conservatively assuming an SD that is 25% larger than that in the pilot data (SD=1.32), Table 1 shows that, with a sample size of 60 per group, two-sided 90% confidence intervals for the mean difference in TMS are anticipated to have a $\frac{1}{2}$ width on the order of ± 0.44 . Thus for TMS, if the mean difference is on the order of 2.0, the 90% confidence interval would be (1.56, 2.44). Estimated SD's for VMWM are not yet available.

Table 2: Expected endpoints of 90% confidence interval (CI) for different scenarios for PVL. Calculations are based on Pearson's Chi-square Method for n=60 (pre-surgical) or, conservatively) n=52 (post-surgical) per group.

Proportion in Control Group	Proportion in Treated Group	True Difference in Proportions	Expected Endpoints of 90% CI
Post-natal PVL (pre-surgical, n=60)			
19.0%	8.5%	10.5%	(0.3%, 20.7%)
19.0%	19.0%	0%	(-11.8%, 11.8%)
Post-operative increase in PVL from baseline (n=52)*			
38.0%	24.0%	14%	(-0.8%, 28.8%)
38.0%	38%	0%	(-14.6%, 14.6%) (-15.7%, 15.7%)
*Conservatively as we expect n=52 to 56 post-operatively			

Next we consider the categorical outcomes. In pilot data ([name], personal communication), 19% of subjects had some PVL prior to surgery and 38% of infants increased the level of

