5. *Binary Secondary Endpoints* will use an exact binomial confidence interval to estimate differences between groups and will be tested using Fisher's Exact test. The confidence level will be set at 90% and the Type I error at 10%. Binary outcomes include
 - a. Presence of WMI pre- and post-operatively
 - b. Completion of MRIs
 - c. Completion of Bayley III at 18 months
6. *Per Protocol and As Treated*
 - a. The analyses of the primary and secondary endpoints described above will be repeated with alternatives to the intention to treat cohort.
 - b. A 'strict' *per protocol* analysis will be used, considering only those subjects who were eligible for the study and who received the treatment as specified in the protocol. This analysis will consider only those subjects who completed at least 90% of their doses at the time of study-based discontinuation (pre-planned at XX weeks or due to earlier labor and delivery). Adherence will be measured in two ways (1) number of medication doses returned and (2) mother's diaries of medication use. Differences in the two measures of adherence will be described.
 - c. As a sensitivity analysis, a 'relaxed' *per protocol* analysis will follow (a) but use completion of 80% of doses instead of 90% of doses, as the cut-off.
 - d. An *as treated* analysis will consider subjects based on their 'dose of progesterone' based on their assignment to control or intervention arm, as well as adherence to study drug in the progesterone arm. In this case we will include dose as a continuous covariate in a regression model, using linear regression for continuous outcomes or logistic regression for binary outcomes. We will assess interactions between dose and treatment arm. This analysis will estimate the effect of the treatment intervention conditional on different levels of adherence to study medication.

7. *Modeling to Adjust for Covariate Imbalance.* Linear or logistic regression analyses of the primary and secondary outcomes will be carried out with adjustment for baseline covariates of fetal brain maturation and development. The covariates will include type of CHD (primary cardiac diagnosis), race, ethnicity, maternal education and socioeconomic status, presence of 22q11 deletions, other identified genetic anomalies and (*APOE*) genotype.
8. Missing data and truncation by death

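### The SAP omits the binary test of post-operative increase in PVL that the protocol specified and sized, and tests only presence of white matter injury before and after surgery

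*SAP*

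**What the plan says.** Protocol 2.2 lists reduction of pre-operative and of post-operative white matter injury as separate secondary aims.

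- **Protocol test.** Section 6.3.2 states: "The null hypothesis that treatment does not reduce the frequency of occurrence of PVL pre-operatively and the rate of increase post-operatively will be tested" with Fisher's exact test, at a 10% Type I error with 90% confidence.
- **Protocol sizing.** Section 6.4 reports from pilot data that "19% of subjects had some PVL prior to surgery and 38% of infants increased the level of" PVL after surgery. Table 2 gives an expected 90% interval for the post-operative increase, 38% versus 24% with 52 per group. It gives no rate or interval for post-operative presence.
- **Protocol endpoint list.** Section 6.2 lists "Presence of PVL on early post-operative brain MRI (categorical y/n" as a secondary endpoint, and 6.3.2 also names post-surgical prevalence as of interest.
- **SAP binary outcomes.** Efficacy Analysis item 5 lists "Presence of WMI pre- and post-operatively", completion of MRIs and completion of the Bayley-III. It does not list increase or new injury.
- **SAP continuous outcomes.** Secondary Endpoints 3.c includes the change in WMI volume from the pre-operative to the post-operative scan. Efficacy item 4 analyses WMI and PVL volumes in the same way as the primary endpoint.
- **Volume analysis set.** Protocol 6.3.2 calls it of interest whether "the volume of PVL (continuous outcome), among those who have PVL at baseline, differs between treatment groups, both at baseline and post-operatively". Section 6.4 uses baseline to mean the pre-surgical scan. The SAP states no such limit.

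**The concern.** The post-operative scan is taken within 10 days of surgery (Protocol 5.2.5). An infant with a lesion before surgery will probably still show it then and be counted as positive, whatever happened in the operating room. A yes/no comparison of post-operative presence therefore adds two things together: injury acquired before surgery, which the pre-operative comparison already covers, and injury acquired around surgery.

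Two consequences follow. A benefit confined to the pre-operative period reappears in the post-operative comparison. A benefit confined to the peri-operative period is diluted by infants who were already positive. The trial is meant to guide outcome selection for a multi-institutional study (Protocol 2), so it matters which of these an estimate reflects.

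The volume clause raises a smaller issue. Pre-operative PVL is measured after randomisation and is itself a treatment outcome. Restricting to infants who have it selects on that outcome and excludes every infant whose first lesion appears after surgery.

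**Working it through.** **Inputs.** Pre-operative PVL 19% in controls and 8.5% if treated; post-operative increase 38% and 24%; 60 per arm pre-operatively and 52 post-operatively (Protocol 6.4, Table 2). Fisher's exact test at 10% (Protocol 6.3.2; SAP item 5). PVL and WMI are treated as the same lesion here, as Protocol 5.2.5 equates overt white matter injury with PVL.

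**1. Reproduce the plan's interval.** Unpooled normal interval: difference ± 1.645 × √[p₁(1−p₁)/n + p₂(1−p₂)/n].
- 38% vs 24%, n = 52: 0.14 ± 1.645 × √(0.2356/52 + 0.1824/52) = 0.14 ± 0.1475, or (−0.75%, 28.75%). Table 2 prints (−0.8%, 28.8%) and the text (−0.7%, 28.7%).
- 38% vs 38%, n = 52: ±15.66%, against ±15.7% printed. The extra ±14.6% in Table 2 is the n = 60 value (14.58%).

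The printed intervals reproduce, and they describe the increase, not presence.

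**2. Model for presence.** Two assumptions are not in the documents. Pre-operative lesions remain visible after surgery. The risk of increase given pre-operative PVL, r, is unknown and is varied from 0 to 1. With q the risk of a new lesion in an infant who had none:
- q = (0.38 − 0.19r)/0.81, which fixes the control increase at 38%
- post-operative presence = pre + (1 − pre) × q

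**3. Pre-operative effect only.** Let r and q be the same in both arms, with pre-operative rates of 19% vs 8.5%. The gap in presence is 0.105 × (1 − q).

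| r | q | Presence, control vs treated | Gap |
|---|---|---|---|
| 0 | 46.9% | 57.0% vs 51.4% | 5.6 points |
| 38% (independent) | 38.0% | 49.8% vs 43.3% | 6.5 points |
| 100% | 23.5% | 38.0% vs 30.0% | 8.0 points |

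In the independent case the exact Fisher test (n = 52 per arm, 10%) rejects 12.0% of the time on presence and 6.1% on increase, the latter being its rejection rate under the null.

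**4. Effect on increase only.** Pre-operative PVL is 19% in both arms, and increase is 38% vs 24%. In the independent case:
- control presence: 0.19 + 0.81 × 0.38 = 49.8%
- treated presence: 0.19 + 0.81 × 0.24 = 38.4%
- difference 11.3 points, 90% interval about (−4.6%, 27.3%)

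Exact Fisher power is 24% on presence against 38% on increase. As r goes from 0 to 1 (treated r and q both scaled by 24/38), power on presence falls from 33% to 14%.

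**5. Volume restricted to pre-operative PVL.** At 52 per arm: 52 × 0.19 = 9.9 controls and 52 × 0.085 = 4.4 treated. With 10 and 4 infants the 90% t-interval half-width is 1.05 SD. At 60 per arm (about 11 and 5) it is 0.95 SD, against 0.30 SD if all 60 per arm are used.

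**The case against.** The case for leaving the SAP alone has real substance.

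- **Presence is the protocol's own endpoint.** A reader might infer that the SAP invented a replacement. It did not. Protocol 6.2 lists post-operative presence, 6.3.2 then tests increase, and the SAP follows one side of that inconsistency. Item 5 also introduces its list with a word that need not be exhaustive: "The confidence level will be set at 90% and the Type I error at 10%. Binary outcomes include". What remains is that the quantity with a stated test, pilot rate and planned interval does not appear.
- **The SAP keeps a change measure.** A reader might infer that the post-operative aim is tested only on carried-over injury. The WMI volume-change endpoint rules that out. It is not a full substitute, because Protocol 6.3.2 itself describes PVL volume as having a peak at zero and a highly skewed remainder.
- **Presence is valid as randomised.** For a prenatal treatment, less total injury after surgery is a real benefit even if all of it arose before surgery, so a difference in presence is not a false positive. The limit is interpretation: it does not show when the injury was prevented.
- **Wider carry-over figures are not pure carry-over.** Holding increase at 38% in both arms allows gaps from 0 to 10.5 points. Those extremes require the risk of a new lesion among lesion-free infants to differ by arm: 23.5% vs 32.2% (19/81, 29.5/91.5) at zero and 46.9% vs 41.5% (38/81, 38/91.5) at 10.5.
- **Increase is not perfectly clean either.** In step 3, if r = 1 the increase rates are 38.0% vs 30.0%, the same gap as presence; if r = 0 they are 38.0% vs 42.9%. Increase separates peri-operative injury fully only when its risk does not depend on pre-operative status.
- **The volume restriction is not in the SAP.** It is one protocol clause worded as of interest. Protocol 2.2 and 6.2 state volume without it, and 6.3.2 offers a joint model that includes infants without PVL. The documents do not support a claim that the SAP analyses volume in the selected subset; the clause only needs to be expressly superseded.

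**Conclusion.** The concern holds in a limited form. The SAP does not carry forward the binary post-operative increase that Protocol 6.3.2 tests and Table 2 sizes, and gives no reason. Presence answers a different question: total injury by the post-operative scan.

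The 5.6 to 8.0 point carry-over and the power of 24% against 38% are moderate in size. They rest on lesions persisting to the post-operative scan, on the protocol's pilot and planning rates, and on 52 infants per arm. The carry-over range also assumes equal conditional risks in the two arms, and the power comparison assumes independence of increase from pre-operative PVL. Power is low on either measure.

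These are secondary outcomes in an exploratory trial and the primary endpoint is unaffected. The SAP should be corrected because the two documents disagree on a planned test.

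**What to change.** In SAP Efficacy Analysis item 5, add new or increased WMI/PVL from the pre-operative to the post-operative MRI (yes/no) as the binary test of peri-operative injury. Define an increase as it was defined in the pilot data behind the 38% figure, since neither document gives a definition. Keep post-operative presence, labelled as a measure of total injury.

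Add one sentence stating that PVL and WMI volume comparisons include all infants with the relevant scan, zeros included. It should supersede the clause in Protocol 6.3.2 that limits volume to infants with pre-operative PVL, and call that scan pre-operative rather than baseline.

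Both scans are already scheduled, so no new data are needed. The costs are agreeing the definition of an increase and losing infants who lack either scan from that endpoint.

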1.4 Selection of Drugs and Dosages

Progesterone therapy has received approval for prevention of preterm birth. On February 3, 2011, the FDA approved the use of progesterone supplementation (hydroxyprogesterone caproate) during pregnancy to reduce the risk of recurrent preterm birth in women with a history of at least one prior spontaneous preterm delivery.⁴⁸ Recently, the Society for Maternal-Fetal Medicine reviewed the existing data and concluded that existing randomized studies indicate that in women with singleton gestations, no prior preterm birth, and short cervical length, vaginal progesterone, either 90-mg gel or 200-mg. suppository, is associated with reduction in preterm birth and perinatal morbidity and mortality, and can be offered in these cases.⁴⁹ This was rated as Level I evidence and a level A recommendation. Similarly, the Maternal Fetal Medicine Committee of the Society of Obstetricians and Gynaecologists of Canada reviewed the existing data and concluded that on the basis of the data from the RCTs and a meta-analysis, it is recommended: 1) that in cases where the clinician and the patient have opted for the use of progesterone the following dosages should be used: for prevention of preterm birth in women with history of previous preterm birth:17 alpha-hydroxyprogesterone 250 mg IM weekly (level of evidence I-B) or progesterone 100 mg daily vaginally (level of evidence I-A); and 2) for prevention of preterm birth in women with short cervix, progesterone 200 mg daily vaginally (level of evidence I-A).⁵⁰

The proposed study will utilize a transvaginal Bioadhesive Delivery System consisting of progesterone in a polycarbophil-based gel (Crinone 8%; Serono Laboratories, Norwell, MA) which was designed to provide prolonged and controlled release of progesterone after vaginal application.² The labeled indications include secondary amenorrhea, ART in patients who require progesterone supplementation, and ART in patients with partial or complete ovarian failure. An unlabeled use is to reduce the risk of recurrent spontaneous preterm birth in appropriately selected women. The usual dosage is 90 mg (8% gel) once or twice daily. An ongoing multi-institution study to determine if progesterone prophylaxis during pregnancy has long-term neonatal or infant benefit uses a daily natural vaginal suppository (200 mg).⁴⁷ Therapy will be initiated in the early third trimester (24-28 weeks GA). This is a period of rapid

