3.4.2 Exclusion Criteria

- 1) Major genetic or extra-cardiac anomaly other than 22q11 deletion
- 2) Language other than English spoken in the home
- 3) Known sensitivity or listed contraindication to progesterone (known allergy or hypersensitivity to progesterone, severe hepatic dysfunction, undiagnosed vaginal bleeding, mammary or genital tract carcinoma, thrombophlebitis, thromboembolic disorders, cerebral hemorrhage, porphyria)
- 4) Prescription or ingestion of medications known to interact with progesterone (e.g. Bromocriptine, Rifamycin, Ketoconazole or Cyclosporin)
- 5) Maternal use of progesterone within 30 days of enrollment
- 6) History of preterm birth or short cervix (defined as cervical length \leq 25 mm at 18-24 weeks GA necessitating progesterone therapy)
- 7) Multiple gestation
- 8) Maternal contraindication for MRI

Subjects with a known history of non-compliance with medical therapy.

Subjects that do not meet all of the enrollment criteria may not be enrolled. Any violations of these criteria must be reported in accordance with IRB Policies and Procedures.

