4.3 Concomitant Medication

All prior and concomitant medications used by the mother within 30 days prior to the screening visit and through the end of the study will be recorded. The dates of administration, dosage, and reason for use will be included.

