- Head, Face and Neck: Cerebellum, choroid plexus, cisterna magna, lateral ventricles, midline falx, cavum septi pellucidi, third ventricle, corpus callosum, posterior fossa, cerebellum, transcerebellar diameter (in centimeters), profile, nose, nasal bone, orbits, lips and palate.
- Chest-Heart: Four-chamber view, outflow tracts, situs, fetal heart rate and rhythm.
- Abdomen: Stomach (presence, size and situs), kidneys, bladder, umbilical cord insertion into the fetal abdomen, umbilical cord vessel number.
- Spine: Cervical, thoracic, lumbar and sacral spine.
- Extremities: Legs and arms (presence or absence). Femoral and humeral length in centimeters. Other long bone lengths will be obtained as clinically indicated.
- Genitalia (male, female, ambiguous).

Fetal Biometry at Repeat Examination: (ultrasound for growth to be performed at 4 week intervals)

- BPD, HC, FL, HL, AC, EFW.
- Fetal presentation.
- Amniotic fluid index and/or amniotic fluid deepest vertical pocket.
- Placental position (placental position at the initial evaluation may not correlate with its location in the third trimester).

- Maternal cervix (cervical length will be measured transabdominally or transvaginally at each sonographic evaluation until 32 weeks gestation) and presence, location and size of uterine and adnexal masses.

Doppler Ultrasonography:

Doppler color flow mapping with reduced color scale will be used to identify the ductus venosus (DV) and the middle cerebral artery (MCA) and average color scale to locate the umbilical artery (UA) and maternal uterine arteries (UtA). Pulsed- wave Doppler will be used to determine blood flow velocities of the UA, UtA, DV and MCA. The peak systolic velocity, peak diastolic velocity, mean velocity, systolic to diastolic ratio (SD), pulsatility index (PI) resistive index (RI) and UA PI/MCA PI with a mixture from stable signals during fetal apnea will be obtained for each of the aforementioned vessels at the initial evaluation at 24-28 weeks and then every 4 weeks.

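### SAP item 6d sets progesterone dose from arm and study-drug adherence alone, so non-study progesterone after randomisation is ignored and an exposed placebo mother is coded as dose zero

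*SAP*

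**What the plan says.** SAP, Efficacy Analysis, item 6 repeats the primary and secondary analyses with alternatives to the intention-to-treat cohort.

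- **6d, as treated.** Dose of progesterone is set "based on their assignment to control or intervention arm, as well as adherence to study drug in the progesterone arm". It enters a linear or logistic regression as a continuous covariate, and its interaction with arm is to be assessed.
- **6b and 6c, per protocol.** 6b limits the set to eligible subjects treated as the protocol lays down, then gives the working rule: "This analysis will consider only those subjects who completed at least 90% of their doses". 6c lowers the cut-off to 80%. Adherence is taken from returned doses and from diaries.

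The protocol bears on this in four places.

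- Section 3.4.2 excludes "Maternal use of progesterone within 30 days of enrollment". It also excludes a history of preterm birth, or a short cervix found at 18-24 weeks. These are entry criteria, and neither document has an on-study counterpart.
- Section 5.2.1 states that "cervical length will be measured transabdominally or transvaginally at each sonographic evaluation until 32 weeks gestation".
- Section 1.4 reports a professional society's conclusion that, in singleton pregnancies with a short cervix and no earlier preterm birth, vaginal progesterone "is associated with reduction in preterm birth and perinatal morbidity and mortality, and can be offered in these cases".
- Section 4.3 says that medications "used by the mother within 30 days prior to the screening visit and through the end of the study will be recorded", with dates, dosage and reason.

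No SAP analysis uses the medication record or the maternal progesterone levels. Cord-blood progesterone appears only as a descriptive item.

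**The concern.** An as-treated analysis is meant to group mothers by what they took. Under 6d, progesterone from outside the trial is invisible in both arms. In the placebo arm the error is largest: a mother given clinical progesterone has a true dose above zero and an analysed dose of exactly zero. If she also keeps using her placebo kit, the dose count in 6b or 6c accepts her as a compliant control.

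At stake is whether these secondary analyses describe actual exposure. The SAP notes, when introducing the endpoints added after the protocol, that practice and research on progesterone in pregnancy changed during accrual. Endpoints were added for that reason, but the exposure variable does not take account of it.

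**Working it through.** **1. The plan's own figure, for scale.** Protocol 6.4 gives 40 evaluable infants per arm, SD 15 and a two-sided 90% interval. Half-width = t(0.95, 78) × 15 × √(2/40) = 1.665 × 15 × 0.2236 = 5.58, which matches the stated 5.6. The protocol's illustrative difference is 6.0 points.

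**2. Is on-study use foreseeable?** The short-cervix exclusion looks at 18-24 weeks. Entry is at 24-28 weeks, with scans every 4 weeks and cervical length measured until 32 weeks. That leaves two scheduled repeat measurements for entry at 24 weeks (28 and 32) and one for entry at 28 weeks (32). A short cervix first seen then is the situation in which section 1.4 says progesterone can be offered. Section 4.4 leaves preterm labour to standard clinical protocols. So the route exists, but it is narrow.

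**3. How 6d codes her.** Assigned arm is control, and adherence counts only in the progesterone arm, so her dose is zero whatever the medication log shows. On this definition dose is zero for every control. Dose × arm then equals dose, and the interaction that 6d asks for cannot be estimated.

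**4. Effect on the as-treated slope (illustration).** The documents give no exposure rate. Assumptions:

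- true effect of 6 points per full dose;
- equal arms;
- adherence in the progesterone arm uniform from 60% to 100%;
- a share c of placebo mothers exposed to a fraction e of a full dose;
- no confounding.

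Let X be the coded dose and C the uncounted dose in controls.

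- Mean adherence is 0.8, with variance 0.4²/12 = 0.0133.
- E[X] = 0.4 and E[X²] = 0.5 × (0.64 + 0.0133) = 0.3267, so Var(X) = 0.3267 − 0.16 = 0.1667.
- X = 0 wherever C > 0, so Cov(X, C) = −0.4 × 0.5ce = −0.2ce.
- Estimated slope = 6 × (1 − 0.2ce/0.1667) = 6 × (1 − 1.2ce).

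| Placebo mothers exposed | Full dose (e = 1): formula / simulated | Half dose (e = 0.5): formula / simulated |
|---|---|---|
| 5% (2 of 40) | 5.64 / 5.64 | 5.82 / 5.81 |
| 10% (4 of 40) | 5.28 / 5.27 | 5.64 / 5.60 |
| 20% (8 of 40) | 4.56 / 4.52 | 5.28 / 5.26 |

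The simulation used 400,000 mothers per arm. Coding the true dose gave slopes of 5.96 to 5.99 in the same runs.

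**The case against.** The strongest reply has four parts.

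- **6b has a further condition.** It requires treatment as the protocol specifies, and a placebo mother on open-label progesterone might be said to fail that. The reading is possible, so it is too strong to say that 6b certainly keeps her. But the protocol has no on-study rule for her to breach, and the SAP turns the phrase into a dose count only. If she stops her placebo, she leaves the set by that count. None of this touches 6d.
- **The event should be uncommon.** Prior preterm birth and a short cervix known by 24 weeks are the main indications the protocol describes, and both are excluded. This stands, and it limits the size of the problem.
- **6d states its aim as the effect conditional on adherence to study medication, not total exposure.** That is fair. Even so, the item is labelled as treated and its variable is called a dose of progesterone, so zero is the wrong value for an exposed mother.
- **The direction of bias is uncertain.** Mothers given progesterone for a short cervix have a higher preterm risk, and protocol 1.5.6 links earlier birth to worse outcomes. Exposed controls could score lower and widen the difference. This stands: the attenuation shown above ignores confounding by indication. Removing such mothers after randomisation also brings its own selection risk.

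**Conclusion.** The point holds for the exposure variable in 6d and, as an ambiguity, for the per-protocol sets in 6b and 6c. With 5% to 20% of placebo mothers exposed, a true slope of 6 would be estimated at about 5.6 to 4.5 for full-dose exposure, or 5.8 to 5.3 for half-dose. This rests on an assumed rate, assumed adherence and no confounding. The shifts are modest beside a half-width of 5.6. The analyses affected are secondary, and keeping every mother in her randomised arm is correct for the primary analysis.

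Three stronger readings are tempting and are not supported.

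- **That about 7% contamination pulls the interval across zero.** This comes from (6 − 5.58)/6 = 6.9%, about 3 of 40 mothers. The 5.58 belongs to the full 40-per-arm cohort analysed as randomised, which this point leaves alone. Per-protocol sets are smaller: at 34 per arm the half-width is 1.668 × 15 × √(2/34) = 6.07, so a difference of 6.0 already includes zero with no contamination. The figure also assumes full benefit from progesterone that may start only after a 28- or 32-week scan.
- **That the interacting-drug exclusion ("Prescription or ingestion of medications known to interact with progesterone") raises the same problem.** Such a drug does not make a placebo mother exposed to progesterone, and the documents show no consequence for the analysis.
- **That these analyses decide whether a larger trial follows.** Protocol 6.4 ties that judgement to the intention-to-treat interval, and 7.1.4 places compliance among secondary analyses.

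**What to change.** Leave the intention-to-treat analysis unchanged. Then:

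1. From the section 4.3 medication log, derive an indicator of non-study progesterone between randomisation and delivery, with dates, and report it by arm.
2. In 6d, build exposure from study drug plus recorded non-study progesterone in both arms, in a common dose unit or, failing that, with a yes/no indicator.
3. Keep 6b and 6c, state how such mothers are handled, and repeat both without them as a sensitivity analysis.

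Maternal serum levels are a poor substitute for the log, since protocol 1.5.4 says they will not reflect fetal concentrations after vaginal dosing.

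The cost is some SAP wording and one derived variable from data already collected. The downsides are slightly smaller per-protocol sets in the sensitivity version, and possible selection or confounding by indication. The report should therefore give the recorded reason for use and avoid claiming a direction of bias. Whether non-study progesterone should be permitted during the trial is a clinical question that is not judged here.
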